##### **4.8.2 Adverse Events**

AEs will be coded using the Medical Dictionary for Regulatory Activities (MedDRA) Version 19.0.

Treatment-emergent adverse events (TEAEs) will be tabulated and are defined as those AEs that either start or worsen in severity on or after the date/time of first dose of study treatment and on or before the final protocol required visit. In general, it is Week 18 Visit and 14 days after the date of last dose of study treatment. The TEAEs are defined as those adverse events that started after first injection up to 14 days post-last dose.

Where dates are missing or partially missing, AEs will be assumed to be treatment-emergent, unless there is clear evidence (through comparison of partial dates) to suggest

that the AE started prior to the first dose of study treatment or more than 14 days after the last dose of study treatment.

Partial AE and concomitant medication start dates will be imputed as follows:

1. If the year (and month and day) is unknown, the date will be imputed as the date of first intake of study treatment if this is possible (i.e., the event end date is not prior to treatment start date).
2. If the month and day is unknown then:
  - a. If the year matches the first dose date, then impute the month and day of the first dose date.
  - b. If the year is earlier than the first dose date or the first dose date is not available (subject is not dosed) and matches the year of informed consent date, then impute the month and day of the informed consent date;
  - c. Otherwise, assign January 1.
3. If the day is unknown then:
  - a. If the month and year match the first dose date, then impute the day of the first dose date.
  - b. If the month and year are earlier than the first dose date or the first dose date is not available (subject is not dosed) and matches the month and year of the informed consent date, then impute the day of the informed consent date;
  - c. Otherwise, assign '1'.

Partial AE stop dates will be imputed as follows:

1. If the year is unknown, the date will not be imputed and will be assigned a missing value.
2. If the month is unknown, then assign December.
3. If the day is unknown, then assign the last day of the month.

For all other settings (eg. year missing, but day and month available etc.), imputation strategies will be reviewed and decided in the ongoing data cleaning and sponsor meetings.

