If the start and/or stop dates of medications other than study treatments are missing or partially missing, the dates will be compared as far as possible with the date of first study treatment administration.

If not specified, observed data approach will be performed.

The AE will be summarized using MedDRA system organ class (SOC) and preferred term (PT). All AE summaries will provide the number of subjects reporting at least one AE and the total number of events reported. The following summaries will be provided:

- A summary of the number and percentage of subjects reporting at least one TEAE, drug-related TEAE, TEAE leading to withdrawal, serious adverse event (SAE), drug-related SAE, SAE leading to withdrawal and death by treatment group.
- A summary of the number and percentage of subjects reporting a TEAE by treatment group, SOC, and PT
- A summary of the number and percentage of subjects reporting a drug-related TEAE by treatment group, SOC, and PT
- A summary of the number and percentage of subjects reporting a treatment-emergent SAE by treatment group, SOC and PT
- A summary of the number and percentage of subjects reporting a drug-related treatment-emergent SAE by treatment group, SOC, and PT
- A summary of the number and percentage of subjects reporting a drug-related TEAE leading to withdrawal by treatment group, SOC, and PT
- A summary of the number and percentage of subjects reporting a TEAE leading to withdrawal by treatment group, SOC, and PT
- A summary of the most common TEAEs by treatment group and PT (reported by >10% of subjects in any treatment group).
- A summary of the number and percentage of subjects reporting a TEAE by treatment group, severity, SOC and PT
- A summary of the number and percentage of subjects reporting a TEAE by treatment group, relationship, SOC and PT

AE summaries will be ordered alphabetically for SOC, and PT within SOC.

For each subject and each AE, the worst severity recorded will be attributed and used in the by-severity summaries. Similarly, the worst causality (most related to treatment) will be attributed and used in the by-causality summaries. If severity or causality is missing, data will be treated as observed

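### Leaving missing AE causality or severity as observed keeps such events out of the drug-related counts and severity levels: a minor, non-conservative choice in SAP 4.8.2

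*SAP*

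**What the plan says.** Section 4.8.2 of the current SAP version sets three rules that bear on incomplete AE records.

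- **Missing classification:** "If severity or causality is missing, data will be treated as observed". This agrees with the section's general default: "If not specified, observed data approach will be performed".
- **Repeat records of the same AE:** "For each subject and each AE, the worst severity recorded will be attributed and used in the by-severity summaries". Causality is handled in the same way, taking the most strongly related of the values on record.
- **Missing dates:** "Where dates are missing or partially missing, AEs will be assumed to be treatment-emergent, unless there is clear evidence". Such evidence has to place the onset ahead of treatment or beyond a 14-day window following its end.

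The same section plans tables that need a causality or severity value. One is "A summary of the number and percentage of subjects reporting a drug-related TEAE by treatment group, SOC, and PT". The others are its counterpart for drug-related SAEs, a drug-related TEAE table restricted to events leading to withdrawal, and tables of TEAEs broken down by severity and by relationship. Section 4.8.3 adds AEs leading to death by severity. No row for missing values is defined for any of them.

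The rule on missing severity and causality stands in all three SAP versions in the file, and the Amendment 3 list of changes does not touch it.

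**The concern.** A missing value has no observed value to use. If nothing is imputed, an event without a causality entry cannot enter a drug-related count, and an event without a severity entry cannot be placed in any severity level. For the drug-related tables, a gap in the record then works in the drug's favour. Elsewhere in the section, doubt about timing, or between several recorded values, is settled against the drug. The SAP gives no reason for the difference.

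Safety and tolerability over the 6-week period are a secondary objective (section 2.2), and groups are planned at 12 subjects (section 4.10). With groups that small, a single unclassified event can visibly change a drug-related percentage by dose. The primary haemoglobin analysis is not affected.

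**Working it through.** The SAP gives no figure on this point. In particular, it does not state how many causality or severity values are, or are expected to be, missing. The check is therefore a reading of the rules plus simple proportions.

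**Step 1: where an unclassified event goes.** Take a TEAE with no causality and no severity value on any of its records.

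| Output (section) | Counted? |
|---|---|
| Any TEAE; TEAE by SOC and PT; most common TEAEs (4.8.2) | Yes |
| SAEs, and TEAEs leading to withdrawal, without restriction to drug-related (4.8.2) | Yes, if it qualifies |
| Special-interest AE summaries (4.8.2) | Yes, if the term qualifies |
| By-subject AE listing, which shows severity and causality (4.8.2) | Yes |
| Drug-related TEAE, drug-related SAE, drug-related TEAE leading to withdrawal (4.8.2) | No |
| TEAE by severity and TEAE by relationship (4.8.2) | In no defined category |

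If another record of the same AE carries a value, the worst-recorded rule classifies the event and the gap has no effect.

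**Step 2: size per subject.** Inputs: 12 subjects per group (section 4.10) and m, the number of subjects in a group who have a TEAE with missing causality and no other drug-related TEAE. The SAP does not give m.

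Shift in the group's drug-related rate = m/12.

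- m = 0: 0 points
- m = 1: 1/12 = 8.3 points
- m = 2: 2/12 = 16.7 points

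Illustration, assuming 2 of 12 subjects have a recorded drug-related TEAE:

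- as observed: 2/12 = 16.7%
- missing counted as drug-related, m = 1: 3/12 = 25.0%
- missing counted as drug-related, m = 2: 4/12 = 33.3%

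**Step 3: the denominator.** Section 4.2 bases percentages on the number of subjects providing data at the relevant time point. It is not stated whether a subject whose only event lacks causality provides data for the drug-related table. With m = 1 in the illustration, the reported figure is 2/12 = 16.7% if the subject stays in and 2/11 = 18.2% if not. Two programmers could follow the same text and produce different tables.

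**The case against.** The strongest reply is that the SAP states a rule in advance and is consistent with itself. The date rule decides whether an event is treatment-emergent. The worst-value rule chooses among values that were recorded. Neither addresses a classification that is absent. The contested sentence matches the section's observed-data default, and the section does not impute everything: an AE stop date with an unknown year is left missing. This stands, so a reader who infers that section 4.8.2 contradicts itself goes further than the text allows.

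A reader might also infer that these events disappear from the safety report. They do not: the overall tables, special-interest summaries and listing keep them, and only the classified counts lose them. Nor is there a stand-alone table of severe TEAEs to be understated; severe is one level of the by-severity table.

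The wording could also be read as allowing a row for missing values in the by-severity and by-relationship tables. The SAP neither defines nor excludes one. That reading would help those two tables, but it would still leave the event out of the drug-related counts.

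Finally, counting missing values as worst case is not automatically cautious when arms are compared, because placebo events would be reclassified too. This also stands, and it is a reason to treat severity differently from causality in the remedy. Missing severity coded as severe is the more debatable of the two assignments.

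**Conclusion.** The point holds as a minor one. Followed literally, the rule keeps TEAEs with no causality value on any record out of the drug-related TEAE, SAE and withdrawal counts, and leaves those with no severity value in no severity level. That is a non-conservative choice beside the section's other handling rules, not an error of fact or an inconsistency.

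The size is 8.3 percentage points per affected subject in a group of 12. This rests on the planned group size being reached and on the subject having no other drug-related TEAE. The total effect cannot be stated, because the number of missing values is unknown and may be zero. The SAP ties no decision rule to drug-related or severity-specific AE rates, so no study conclusion is shown to depend on this.

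**What to change.** Before unblinding, replace the sentence in section 4.8.2 with a rule to this effect:

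- In the drug-related summaries, count a TEAE whose causality is missing on all records as drug-related, in every arm including placebo.
- In the by-severity table, show events with no severity value in a separate *Missing* row, and give a sensitivity count that treats them as severe.
- Keep all treated subjects of the group in the denominator of these tables.
- Show the values as missing in the by-subject listing.

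The cost is a short SAP edit, one table row and one sensitivity count, with no new data. The downside is that a few events, including placebo events, may be over-attributed. This could narrow or widen differences between arms, and the listing will show where it happened.

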#### **4.8.3 Deaths, Serious Adverse Events, and Other Significant Adverse Events**

Other significant AEs are those AEs reported as leading to withdrawal from study. The summaries of SAEs and AEs leading to withdrawal from study are described in section 4.8.2.

A summary of the number and percentage of deaths during the study will be provided by treatment group

A summary of the number and percentage of subjects Adverse Events Leading to Death by treatment group, severity, SOC and PT

A by-subject listing of all deaths that occurred during the study will be provided.

#### **4.8.4 Clinical Laboratory Evaluation**

##### **4.8.4.1 Liver function abnormality**

A summary of Liver function abnormality by visit will be provided by treatment group. Any subject with at least one of the following liver function abnormalities is summarized:

- ALT  $\geq 2x$  and  $< 3x$  ULN
- AST  $\geq 2x$  and  $< 3x$  ULN
- Bilirubin  $\geq 2x$  and  $< 3x$  ULN
- ALT  $\geq 3x$  ULN
- AST  $\geq 3x$  ULN
- Bilirubin  $\geq 3x$  ULN

##### **4.8.4.2 Serum and urine pregnancy tests**

Serum pregnancy test for females of childbearing potential will be performed at the screening visit and will be used for subject’s inclusion / exclusion. Urine pregnancy test will be performed at the baseline visit and used for subject’s initiation of study drug.

Additional pregnancy tests may be conducted during the study to establish the absence of pregnancy based on the investigator's clinical judgment or as required by local regulations.

A by-subject listing of serum and urine pregnancy tests will be provided.

#### 4.8.4.3 Coagulation tests

Coagulation tests will be performed at the baseline visit. The following variables will be analyzed.

- prothrombin time
- partial thromboplastin time
- international normalized ratio

A summary of baseline coagulation test results will be provided by treatment group.

A by-subject listing of coagulation tests will be provided.

#### 4.8.4.4 Folate and vitamin B12

Folate and vitamin B12 tests will be performed at the screening visit and will be used for subject's inclusion / exclusion.

A by-subject listing of folate and vitamin B12 tests will be provided.

#### 4.8.4.5 Urine albumin-to-creatinine ratio (uACR)

Urine albumin-to-creatinine ratio (uACR) will be evaluated at baseline visit.

A by-subject listing of uACR will be provided.

#### 4.8.4.6 Complete Blood Count (CBC)

The following components of the CBC are described in Efficacy / PD analysis section.

- Hb
- Hematocrit
- RBC count
- Automated Reticulocyte Count (both absolute and percent).

The following components of the CBC will be analyzed:

- Mean Corpuscular Volume
- Mean Corpuscular Hb
- Mean Corpuscular Hb Concentration
- Red Cell Distribution Width
- White Blood Cell count with differential (neutrophils, bands, lymphocytes, monocytes, eosinophils, and basophils)
- Platelets

The following summaries will be provided:

- A summary of each component of the CBC by treatment group and time point
- A summary of the change from baseline in each component of the CBC by treatment group and time point
- A summary of the number and percentage of subjects experiencing abnormal values by component of CBC, treatment group and time point.

A by-subject listing of CBC will be provided by treatment group.

#### 4.8.4.7 Chemistry and estimated glomerular filtration rate (eGFR)

The following laboratory parameters will be analyzed:

- Sodium
- Potassium
- Bicarbonate
- Chloride
- Calcium
- Phosphorus
- Glucose
- Creatinine
- Blood Urea Nitrogen
- Creatine Phosphokinase
- Uric Acid
- Albumin
- Total Protein
- Total Bilirubin
- Alkaline Phosphatase
- Alanine Aminotransferase (ALT)
- Aspartate Aminotransferase (AST)
- Lactate Dehydrogenase
- Total cholesterol
- Estimated Glomerular Filtration Rate (eGFR) (calculated from serum creatinine)

The following summaries will be provided:

- A summary of Chemistry and eGFR by treatment group and time point
- A summary of the change (absolute and percent) from baseline in Chemistry and eGFR by treatment group and time point
- A summary of the number and percentage of subjects experiencing abnormal values by laboratory parameter, treatment group and time point

The eGFR will be calculated from serum creatinine by following formula:

$$\begin{aligned} \text{eGFR(mL/min/1.73m}^2\text{)} \\ = 194 \times (\text{Scr in mg/dL})^{-1.094} \times (\text{Age})^{-0.287} \times (0.739 \text{ if female}) \end{aligned}$$

A by-subject listing of Chemistry and eGFR will be provided by treatment group.

#### 4.8.4.8 C-reactive protein and Vascular Endothelial Growth Factor (VEGF)

The following summaries will be provided:

- A summary of C-reactive protein (CRP) and VEGF by treatment group and time point
- A summary of the change (absolute and percent) from baseline in CRP and VEGF by treatment group and time point

The effect of treatment in terms of the change from baseline to Week 6 in CRP and VEGF will be analyzed using ANCOVA. The statistical model will assess the main effect of treatment, adjusted for baseline measurement. Three post-hoc pairwise comparison, i.e., Placebo vs 150 mg, placebo vs 300 mg, and placebo vs 600 mg, will be done. Unadjusted ANOVA will be performed for sensitivity.

A by-subject listing of CRP and VEGF will be provided by treatment group.

### 4.8.5 Vital Signs, Physical Findings and Other Observations Related to Safety

#### 4.8.5.1 Vital Signs

The following variables will be analyzed:

- Blood Pressure (Systolic / Diastolic)
- Heart Rate
- Respiratory Rate
- Body Temperature

The following summaries will be provided:

- A summary of each vital sign parameter by treatment group and time point.
- A summary of the change (absolute and percent) from baseline in each vital sign parameter by treatment group and time point.

Any findings of treatment-emergent vital sign abnormalities will be handled as adverse event and reported in AE tables / listings.

A plot showing the mean blood pressure over time within each treatment group. 95% CI of these means will be shown as error bar and sample size in each group at each time point will be shown.

A by-subject listing of vital sign parameter with reference ranges will be provided.

#### 4.8.5.2 12-lead ECG

The following variables will be analyzed at the Baseline Visit:

- Heart rate
- PR interval
- QT interval
- QRS interval

- QTc (corrected)
- Overall result

A summary of each ECG parameter will be provided by treatment group.

A by-subject listing of 12-lead ECG results will be provided.

#### 4.8.5.3 Physical Examination and Weight Assessment

Physical Examination and Weight Assessment will be performed at the Screening Visit and used for subject's inclusion / exclusion. Weight and height will be reported in demographic tables and listings.

#### 4.8.6 Safety Monitoring (Independent Data Monitoring Committee [IDMC], Data Monitoring Committee [DMC], Data and Safety Monitoring Board [DSMB])

Not applicable. No change of study conduct based on preliminary analysis result is planned.

### 4.9 Other Analyses

#### 4.9.1 PK Analysis

The following summary will be provided:

- The summary of pre-dose plasma concentrations of vadadustat and its metabolites at Week 4 Visit by treatment group.
- Box plots of pre-dose plasma concentrations of vadadustat and its metabolites at Week 4 Visit by treatment group.
- Dose-normalized box plots of pre-dose plasma concentrations of vadadustat and its metabolites at Week 4 Visit by treatment group.

Concentrations below the limit of quantification (BLQ) will be replaced by the 0 for the calculation of descriptive statistics. So concentration contains BLQ values are treated as 0 for all summary statistics except geometric mean and its related parameters.

By-subject listings of pre-dose plasma concentrations of vadadustat and its metabolites will be provided by treatment group.

#### 4.9.2 Treatment-Emergent Outliers analysis

The purpose of this analysis is to identify the treatment Emergent outliers by each prescribed dose at each period. The definition of prescribed doses is the subjects with latest dose amount at planned visit when dose change. e.g. if at Week 2 with dose 600 mg and dose reduced to 450 mg at week 4, then visit of prescribed dose for VADA 450 was assigned to Week 4.

However, if subject had dose reduction on 150 mg or had interruption of study medication, the prescribed dose will be considered as 0 mg.

Only treatment-emergent outliers will be counted but outliers at the baseline and screening visits will be excluded.

The following components will be analyzed by primary efficacy period and dose adjustment and maintenance period for all subjects and for subjects with non-elevated values at baseline:

- Non-elevated at baseline definition for each component
  - Systolic Blood Pressure <140 mmHg
  - Diastolic Blood Pressure <90 mmHg
  - Heart Rate <100 bpm
  - Potassium <4 mEq/L

The following component with following criteria will be applied.

- Systolic Blood Pressure
  - Any SBP  $\geq 160$  to <180 mmHg
  - Any SBP  $\geq 180$  mmHg
  - Any SBP increase from baseline  $\geq 20$  to <40 mmHg
  - Any SBP increase from baseline  $\geq 40$  mmHg
- Diastolic Blood Pressure
  - Any DBP  $\geq 100$  to <110 mmHg
  - Any DBP  $\geq 110$  mmHg
  - Any DBP increase from baseline  $\geq 10$  to <20 mmHg
  - Any DBP increase from baseline  $\geq 20$  mmHg
- Heart Rate
  - Any pulse  $\geq 100$  to <120 bpm
  - Any pulse  $\geq 120$  bpm
  - Any pulse increase from baseline  $\geq 20$  to <30 bpm
  - Any pulse increase from baseline  $\geq 30$  bpm
- Potassium
  - Any Potassium >5.5 to 6.0 mEq/L
  - Any Potassium >6.0 to 6.5 mEq/L
  - Any Potassium >6.5 mEq/L
  - Any Potassium increase from baseline >0.5 to 1.0
  - Any Potassium increase from baseline >1.0 to 1.5 mEq/L
  - Any Potassium increase from baseline > 1.5 mEq/L

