### 3 INVESTIGATIONAL PLAN

#### 3.1 Overall Study Design and Plan

[figure not shown]
This is a Phase 2, randomized, double-blind, placebo-controlled, dose-finding study to assess the efficacy, safety, tolerability, PK, and PD of orally administered vadadustat in Japanese subjects with anemia secondary to NDD-CKD.

The study has a planned enrollment of 48 subjects to be enrolled at approximately 25 sites in Japan. There will be 16 subjects in each of the 3 tablet-count groups.

An overview of the study design is presented in [Figure 1](#).

Figure 1: Overview of Study Design

\* For subjects who develop an excess Hb response during the primary efficacy period, the number of tablets of study drug will be decreased (see Section 8.2.4). For these subjects, the number of tablets of vadadustat initiated at the Week 6 visit will be lower than indicated.

The study will include the following periods:

- Eligibility screening period (up to 4 weeks)
- Primary efficacy period (6 weeks; Weeks 1 to 6)
- Dose adjustment and maintenance period (10 weeks; Weeks 7 to 16)
- Follow-up period (2 weeks; Weeks 17 and 18)

Subjects will participate in a screening period (4 days to 4 weeks) to determine study eligibility, and eligible subjects will be randomized following the screening period.

Using a central randomization system, subjects will be randomized 1:1:1 to receive 1, 2, or 4 tablets at their baseline visit (Day 1). Within each tablet-count group, subjects will be randomized 3:1 to receive vadadustat (150, 300, or 600 mg vadadustat) or placebo. See the protocol section 8.2.2 for information regarding the randomization scheme.

Study drug treatment will be administered during a 6-week primary efficacy period. See the protocol section 8.2.4 for information on study drug administration. The primary efficacy period includes fixed-dose treatment to establish a dose-response relationship. However, if Hb level increase rapidly or if the Hb level exceeds 13.0 g/dL, the study drug dose can be decreased or interrupted (see the protocol section 8.2.4).

After completing the primary efficacy period, subjects will continue to a 10-week dose adjustment and maintenance period (see the protocol section 8.2.5). Subjects receiving placebo will be switched to vadadustat, and study drug dose will be adjusted to achieve a target Hb of 10.0-12.0 g/dL based on dose adjustment guidelines (see the protocol section 8.2.5).

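### Outlier thresholds for blood pressure, heart rate and potassium are tabulated only by prescribed dose, which Hb response can change after Day 1, so Weeks 1–6 give no randomised comparison on these cut-offs

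*SAP*

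**What the plan says.** All references are to the current SAP text, as amended by Amendment 3.

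- **Grouping (4.9.2).** "The purpose of this analysis is to identify the treatment Emergent outliers by each prescribed dose at each period". The dose is defined thus: "The definition of prescribed doses is the subjects with latest dose amount at planned visit when dose change". The worked example is a subject moved from 600 mg to 450 mg at Week 4.
- **Zero dose (4.9.2).** For a subject whose drug is interrupted, or who is reduced from 150 mg, "the prescribed dose will be considered as 0 mg". Where placebo subjects are placed is not stated.
- **Periods (4.9.2).** "The following components will be analyzed by primary efficacy period and dose adjustment and maintenance period", each for all subjects and for those not elevated at baseline.
- **What moves the dose (3.1).** In Weeks 1–6, "if Hb level increase rapidly or if the Hb level exceeds 13.0 g/dL, the study drug dose can be decreased or interrupted". After Week 6, "Subjects receiving placebo will be switched to vadadustat, and study drug dose will be adjusted to achieve a target Hb of 10.0-12.0 g/dL".
- **Output by treatment group elsewhere.** For vital signs, 4.8.5.1 gives "A summary of each vital sign parameter by treatment group and time point", together with changes from baseline and a mean blood-pressure plot. Section 4.8.4.7 gives potassium values, changes and abnormal counts. Section 4.8.2 gives adverse-event tables, with hypertension and hyperkalemia terms among the events of special interest.

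**The concern.** Assigned treatment is randomised; prescribed dose after Day 1 is not. A subject leaves the 600 mg row because Hb rose quickly or went too high, so the 450 mg row collects strong responders and the 600 mg row keeps the rest. If Hb response is related to blood pressure, pulse or potassium for any reason, the rows will differ even when the drug has no effect on those measures. They can equally mask an effect that is real.

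The 0 mg row has a further problem. It receives vadadustat subjects whose dose was withdrawn, and nothing in the text separates them from placebo, so it cannot be assumed to be a clean control row.

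Weeks 1–6 are the only placebo-controlled part of a study meant to define a Phase 3 starting dose. A reader shown outliers by dose will take the pattern as dose-related safety, which these rows cannot support.

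**Working it through.** **1. Group sizes.** Section 3.1 randomises 48 subjects 1:1:1 by tablet count, and "Within each tablet-count group, subjects will be randomized 3:1 to receive vadadustat" or placebo. So 48/3 = 16 per tablet count; active 16 × 3/4 = 12 per dose; placebo 16 × 1/4 = 4 in each of three counts, or 12 in all. This agrees with the 12 per group in 4.10. The SAP gives no numerical figure for the outlier tables themselves.

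**2. Are the thresholds applied by group anywhere?** Section 4.9.2 has SBP 4 + DBP 4 + heart rate 4 + potassium 6 = 18 rows, all by prescribed dose. Sections 4.8.2, 4.8.4.7 and 4.8.5.1 report by treatment group but use none of these cut-offs.

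**3. Composition of the rows in Weeks 1–6.** Assume a fraction q of each vadadustat group drops by 150 mg, and that placebo is placed at 0 mg (the SAP does not say so). The 0 mg row then holds 12 + 12q subjects, of whom 12q are on vadadustat.

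| q | 0 mg | 150 mg | 300 mg | 450 mg | 600 mg | Vadadustat share of 0 mg row |
|---|---|---|---|---|---|---|
| 10% | 13.2 | 12 | 10.8 | 1.2 | 10.8 | 1.2/13.2 = 9% |
| 25% | 15 | 12 | 9 | 3 | 9 | 3/15 = 20% |
| 40% | 16.8 | 12 | 7.2 | 4.8 | 7.2 | 4.8/16.8 = 29% |

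**4. Illustration of the distortion.** Assumptions, none from the SAP:
- no drug effect on SBP;
- SBP change normal with mean 0 and SD 12 mmHg;
- correlation r = 0.3 to 0.5 with Hb response;
- the top fraction q of Hb responders in the 600 mg arm is cut to 450 mg, and each subject is counted in the row of the latest dose.

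Formulas:
- Every randomised arm: p = P(Z ≥ 20/12) = P(Z ≥ 1.667) = 4.8%.
- 450 mg row: a = P(SBP rise ≥ 20 | Hb response in top q), from the bivariate normal distribution.
- 600 mg row: (p − q·a)/(1 − q). For q = 10% and r = 0.3, (4.78 − 0.10 × 11.8)/0.90 = 4.0%.

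| q | 450 mg row (r = 0.3 to 0.5) | 600 mg row (r = 0.3 to 0.5) | Randomised 600 mg arm |
|---|---|---|---|
| 10% | 11.8% to 18.7% | 4.0% to 3.2% | 4.8% |
| 25% | 9.2% to 12.6% | 3.3% to 2.2% | 4.8% |
| 40% | 7.8% to 9.7% | 2.8% to 1.5% | 4.8% |

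**5. In subjects.** At q = 10% the 450 mg row has 1.2 subjects and expects 1.2 × 0.118 to 1.2 × 0.187 = 0.14 to 0.22 events. The 600 mg row has 10.8 subjects and expects 10.8 × 0.040 to 10.8 × 0.032 = 0.43 to 0.35. The intact arm expects 12 × 0.048 = 0.6.

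**6. Second model.** A simulation of 4,000 trials of 48 subjects used a 20% base risk, log-odds rising by 1 per g/dL of Hb response, no dose effect and q = 25%, with placebo at 0 mg. The rows show 25.0% (0 mg), 22.0% (150), 16.9% (300), 37.3% (450) and 16.9% (600), against about 22% in every randomised group. The 600 mg row looks safer than 0 mg through the grouping alone.

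**The case against.** **Much by-group safety output remains.** A reader might infer that the placebo comparison of blood pressure and potassium is lost altogether. The documents do not support that. The means, changes, plot, abnormal counts and adverse-event tables listed above are all by treatment group. Section 4.8.5.1 also sends treatment-emergent vital-sign abnormalities into the adverse-event tables, so a categorical route by group exists. This stands. But those tables depend on what is reported as an event and apply none of the 4.9.2 cut-offs.

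**The numbers are small and the inputs assumed.** This also stands. With 10% cut, the 450 mg row is about one subject. The large percentages there show the direction of the bias; they do not predict the result.

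**Tabulating by dose taken is a fair descriptive question.** Section 4.9.2 sits under other analyses and has no test or decision rule, and the starting-dose objective is tied to the Hb dose-response. Agreed; this is a reason to keep and label the tables, not to leave them as the only ones.

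**After Week 6 nothing can be restored.** Placebo subjects then receive vadadustat, so no tabulation gives a concurrent placebo comparison. Correct; the avoidable loss is confined to Weeks 1–6.

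**Conclusion.** The point holds, narrowly. For the 18 threshold rows, the SAP plans no tabulation that preserves randomisation in the one period where that is possible, and the rows it does plan are sorted by Hb response. Because starting dose is randomised and Hb can only lower or interrupt it in Weeks 1–6, the distortion is partial. Its size depends on the fraction of subjects whose dose changes and on the correlation with Hb response, and the SAP gives neither. Under the SBP assumptions above, a uniform 4.8% becomes 12–19% at 450 mg and 3–4% at 600 mg with 10% cut, and 8–10% and 1.5–3% with 40% cut.

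Two further inferences go too far. The SAP does not say that placebo is pooled into the 0 mg row, only that nothing keeps it separate. And the Week 6 ANCOVA planned for CRP and VEGF (4.8.4.8) does not make its absence for blood pressure and potassium an error; such a model is not needed to cure the grouping. The primary analysis is unaffected.

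**What to change.** In 4.9.2:

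1. For the primary efficacy period, tabulate the same 18 rows by treatment group (placebo, 150, 300 and 600 mg), for all subjects and for those not elevated at baseline.
2. In the prescribed-dose tables, show placebo separately from vadadustat subjects recoded to 0 mg.
3. Label the prescribed-dose tables descriptive, non-randomised and response-driven.

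The cost is a few sentences of SAP wording and a few extra descriptive tables from data already collected. With 12 per group the new tables should be read as counts. No dosing rule and no other analysis changes.
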